## Missing Data

Missing data for secondary measures will be assessed for quantity and nature of missingness. As secondary analyses are hypothesis generating, whole case analysis will be used even if >5% are missing data. Although the baseline values are also required for the secondary outcome analysis, we anticipate missingness

will be extremely infrequent as REDCap will be used for data collection and missing completely at random (MCAR) so that no bias will be incurred by dropping those cases from the analysis. Participants that drop out prior to completion of protocol will be right censored for survival analyses.

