## **Explanatory Variables to Characterize the Population:**

Demographic and medical variables to characterize the participant population will be collected at baseline and will include age, sex/gender, place of residence, education, postal code, occupation, race and ethnicity, presence of caregiver at residence, duration of radiation therapy, and medical comorbidities and medications. To reduce the time demands placed on participants, a research assistant will collect the variables whenever possible from chart review, and ask participants to provide information on the variables not available from chart review.

Table 1. Measurement Tools and Testing Schedule

Base-	4W	W8	12W	26W
line	`	(100	(100	(160
(100	min)	min)	min)	min)
min)				

Participant Demographic and Medical Information Form	Х				
Participant Personal Information Form	Х				
General Outcomes					
Feasibility and Safety Outcomes		Х	Х	Х	Х
Survival and Progression-Free Survival		Х	Х	Х	Х
EuroQol-5 Dimension 5 Level (EQ-5D-5L)	Х	Х	Χ	Х	Х
Fatigue Severity Scale	Х	Х	Χ	Х	Х
Physical outcomes measures					
Berg Balance Scale	Χ	Х	Χ	Х	X
Timed Up and Go Test	Χ	X	Χ	X	X
3m Walk Test	Х	X	Χ	X	X
The Arm Capacity and Movement Test (ArmCAM)	Х	Х	Χ	Х	Х
Cognitive tests					
Brief Test of Adult Cognition by Telephone (BTACT)	Х	Х	Χ	Х	Х
Brief Visuospatial Memory Test – Revised (BVMT)	Х	Х	Х	Х	Х
Sustained Attention to Response Task (SART)	Х	Х	Х	Х	Х
Wechsler Test of Adult Reading (WTAR)	Х	Х	Χ	Х	Х
Qualitative component					
Semi-structured Interview (telerehab group only)					Х

The majority of our outcome measures are self-report measures, which participants can either complete themselves and/or with assistance from a helper or research study staff based on participants' preferences. The outcome measures can be administered via a REDCap survey link sent to participants to enter their answers directly into REDCap or with assistance from a helper if they need it or via an online videoconference or telephone call between participants and study staff for direct entry of participants' answers into REDCap by research study staff (whichever method participants prefer).

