## **Study Sample Size and Statistical Analysis Sample Size**

A sample of 54 participants, 27 per arm, is planned for this study based upon an expected recruitment rate of a third (33%) of glioma patients seen in recruiting clinics (163 patient per annum). Feasibility trials are recommended to recruit between 20 to 50 participants per arm to adequately investigate if a protocol is feasible or not and a minimum of 22 participants per arm is required for precision

of the variance estimation. Loss to follow-up (LOF) will be analyzed as the primary outcome and the sample size will not be adjusted for LOF.

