## Secondary Outcomes

Secondary outcomes (e.g. balance, mobility, quality of life, mood, etc.) are continuous in nature and will be analyzed using linear regression, adjusted for baseline. Time to all-cause mortality, time to disease specific mortality, and time to disease progression will be analyzed using Kaplan Meier estimators and logrank tests.

Disease and demographic factors that may influence protocol attrition and adherence will be analyzed using a generalized linear mixed effects model with an assumed unstructured covariance matrix structure and robust sandwich estimation.

To assess the safety of the protocol, the number, type, and severity of SA events will be reported as a cumulative incidence and compared between treatment arms using a Poisson regression.

Since these analyses are hypothesis generating, complete-case analyses will be used, p-values will not be listed and 95% confidence intervals of estimates and change scores will be used instead so the study results can be interpreted in context. The standard deviation of changes in secondary outcome measures will be used for sample size calculations for future full-scale studies.

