## Subgroup Analyses

Exploratory subgroup analyses will analyze group differences in demographic factors like age, disease factors such as tumor grade, tumour location and deficit type (e.g. physical, cognitive, communication, etc.) on secondary outcome measures using linear mixed effects modeling for measures repeatedly administered following randomization. As these are exploratory in nature and under-powered to sufficiently detect group differences, effect estimates and their 95% CI will be reported and p-values will not be reported.

Thematic analysis will be used to analyze the collected data. The first five interview transcripts will be initially coded by two members of the research team, and they will then meet to compare their codes. This step will allow for enhanced reflexivity and ensure rigour. A coding framework will be developed and applied to the remaining transcripts.

To facilitate the organization and analysis of the qualitative data, the transcripts, will be entered into NVivo 11. Following this, the codes will be clustered into groups or categories (i.e., codes that share similar meanings) and the predominant themes will be identified.

To maximize credibility and trustworthiness, additional members of the research team will meet with the two members of the research team over several meetings to discuss the developing analysis. New themes will also be discussed. Together, they will explore various thematic maps until consensus is reached and theme labels are agreed upon. The two members of the research team will analyze the remaining data. To protect anonymity, quotes exemplifying the various themes will not include any identifying details on the participants.

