## **Documenting participant withdrawal**

In all circumstances, reasons for withdrawal will be collected and all participants will be followed through to the trial's conclusion with previously stated outcome measures performed (timing is outlined in Table 1), as the main analysis will be an intention to treat analysis. This will, of course, be subject to the participant's continued consent to return for these assessments. Participants who withdraw consent will be advised to follow up with their regular health care provider.

Participants who are withdrawn or withdraw from active treatment will not be replaced.

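### Complete-case regression for the secondary outcomes, however much follow-up is missing, discards observed visits and can bias the contrasts; a repeated-measures model would use them at little cost

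*Protocol*

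**What the plan says.** **Model.** Under Statistical Analysis Plan, Secondary Outcomes, the continuous secondary measures are analysed by linear regression with adjustment for baseline, on complete cases. The reason given is that the analyses are hypothesis generating. Estimates and change scores are reported with 95% confidence intervals and no p-values.

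**Missing data.** The Missing Data section says the amount and nature of missingness will be assessed, but that "whole case analysis will be used even if >5% are missing data". It then says missing baseline values should be very rare because of REDCap, and completely at random, so dropping those cases brings no bias.

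**Follow-up.** The measures are repeated at weeks 4, 8, 12 and 26. Documenting participant withdrawal says withdrawn participants will still be assessed, subject to consent, because "the main analysis will be an intention to treat analysis". Reasons for withdrawal includes becoming unable to complete the intervention or the assessment visits.

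**Mixed model.** Subgroup Analyses specifies "linear mixed effects modeling for measures repeatedly administered following randomization" for the secondary measures, in exploratory subgroup work only.

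**Planning use.** "The standard deviation of changes in secondary outcome measures will be used for sample size calculations for future full-scale studies".

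**The concern.** The protocol makes complete-case analysis the rule at any level of missingness and names no sensitivity analysis. A regression on one follow-up value per person drops a participant who has weeks 4, 8 and 12 but not week 26 from the week-26 contrast, although those scores carry information about the missing one.

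An exploratory purpose is a reason to omit p-values. It is not a reason to accept selection. The no-bias statement is attached to baseline values and rests on the data-capture system, which has no bearing on whether a patient with glioma is well enough to be assessed months later. The protocol itself foresees loss through inability to attend assessments. Participants know their allocation and the two arms make different demands, so loss that depends on condition and differs by arm is credible, though not established.

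At stake are the treatment contrasts the pilot will report as preliminary effectiveness, their precision, and the variance figures passed to the next trial. In addition, the main contrasts and the subgroup contrasts on the same measures would come from different models and different sets of patients.

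**Working it through.** **1. The plan's own figure.** "A sample of 54 participants, 27 per arm, is planned for this study", from "an expected recruitment rate of a third (33%) of glioma patients seen in recruiting clinics" with 163 patients a year. 163 × 0.33 = 53.8 and 163/3 = 54.3; both round to 54, and 54/2 = 27. The figure reproduces. It is a recruitment figure: the protocol gives no SD, correlation, effect size or expected dropout for the secondary outcomes, so steps 3 to 5 rest on assumptions.

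**2. What each stated reason covers.**

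| Reason in the protocol | What it covers | Missing follow-up values? |
|---|---|---|
| Hypothesis-generating purpose | Leaving out p-values | No |
| REDCap capture, completely at random | Missing baseline values | No |
| Amount and nature of missingness assessed | Description | No: the method stays the same whatever is found |

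**3. When complete cases go wrong.** Large-sample simulation: 400,000 participants, five visits, unit SD, AR(1) correlation 0.6 between adjacent visits (so 0.6⁴ = 0.13 between baseline and week 26), true week-26 effect 0.50 SD, and monotone dropout after weeks 4, 8 and 12. Each cell gives the week-26 effect by complete-case baseline-adjusted regression / by a likelihood analysis of all visits.

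| Dropout driven by | 10% lost | 20% lost | 40% lost |
|---|---|---|---|
| Nothing (completely at random) | 0.497 / 0.496 | 0.493 / 0.492 | 0.507 / 0.508 |
| Baseline score only | 0.501 / 0.501 | 0.498 / 0.498 | 0.496 / 0.498 |
| Latest score, same in both arms | 0.487 / 0.501 | 0.476 / 0.499 | 0.461 / 0.503 |
| Latest score, one arm only | 0.535 / 0.498 | 0.564 / 0.494 | 0.641 / 0.501 |
| Latest score, opposite directions by arm | 0.568 / 0.500 | 0.639 / 0.501 | 0.787 / 0.502 |

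At 20% loss the relative error runs from none (first two rows) through (0.476 − 0.50)/0.50 = −5% to (0.639 − 0.50)/0.50 = +28%. Dropout was generated from observed scores, so the likelihood analysis recovers the truth by construction. The table shows what complete cases lose when that assumption holds; it does not show that the assumption holds in this trial.

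**4. Size against sampling error.** With 20% lost from 27 per arm, n = 21.6 per arm. Residual SD = √(1 − 0.13²) = 0.99. The 95% half-width is about 2.02 × 0.99 × √(2/21.6) = 0.61 SD. The largest error at 20% loss is 0.639 − 0.50 = 0.14 SD, well inside that interval.

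**5. The SD for planning.** With equal variances σ² and baseline–follow-up correlation r:
- variance of change = 2σ²(1 − r)
- baseline-adjusted residual variance = σ²(1 − r²)
- ratio = 2(1 − r)/(1 − r²) = 2/(1 + r)

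A baseline-adjusted trial sized on the SD of change is therefore too large by 2/1.5 = 1.33 (33%) at r = 0.5, and by 2/1.7 = 1.18 (18%) at r = 0.7.

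Selection has a small effect. In the same simulation the complete-case SD of change was at most 3% low at 20% loss (1.280 against 1.319) and 5% low at 40% (1.254 against 1.320). Sampling error is larger: the 95% limits for an SD are about −16% and +24% with 54 participants, and −18% and +28% with 43.

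**The case against.** **Bias is not shown.** This stands. A reader might infer that the secondary contrasts will be biased. The protocol does not support that: baseline-adjusted complete-case regression has no material bias when missingness depends only on arm and baseline, and nothing in the document fixes the mechanism or the amount of loss. Any bias would also sit inside wide intervals that are reported without p-values. What remains is that the choice leaves an avoidable risk and discards observed data.

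**Intention to treat is not flatly contradicted.** This also stands. The phrase in Documenting participant withdrawal may refer only to the feasibility outcome, and complete cases compared by randomised arm are not an as-treated analysis. But the assessments that section preserves supply the secondary outcomes, so its scope needs stating.

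**The mixed model is not already the plan's main analysis.** Correct: it is specified for subgroups only. It shows that the method is available to the team, and no more.

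**The SD of change is not a wrong figure.** Correct. Change scores are a planned summary, the next trial's analysis is not in this document, and for a baseline-adjusted trial the SD of change errs towards too large a sample.

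**Complete cases need not fall below the stated minimum.** The Sample Size section says "a minimum of 22 participants per arm is required for precision" of the variance estimate, and 27 × 0.8 = 21.6 invites the inference that a trial just meeting the 80% feasibility bound would miss it. That bound concerns completing the 8-week protocol, and withdrawn participants are still to be assessed. The inference holds only if non-completers also lack outcome data.

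**Mode of assessment.** The text below Table 1 says "The majority of our outcome measures are self-report measures", whereas eight of the 11 measures repeated in the visit lists are performance tests. That is a separate descriptive slip. The protocol does not say which tests need a live evaluator, so it does not show which measures would go missing.

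**The remedy has limits.** A mixed model assumes data missing at random and, left unqualified, extrapolates scores beyond death.

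**Conclusion.** The concern holds in a limited form. The protocol fixes complete-case regression for the secondary outcomes at any level of missing follow-up, on grounds that do not apply to follow-up values, and so sets aside post-baseline data it has taken care to collect. Bias is possible, mainly when missingness depends on post-baseline status differently by arm. Under the assumed settings the error ranged from none to +28% of a 0.50 SD effect at 20% loss; the true size cannot be derived from the document. The planning point is one of completeness: without the residual SD or the correlation, a baseline-adjusted successor could be oversized by 18% to 33% for r between 0.7 and 0.5, assuming equal variances. Importance is moderate, because these outcomes are secondary and exploratory and the feasibility outcome is untouched. The change is worth making because it needs no new data.

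**What to change.** - **Secondary Outcomes:** make a linear mixed model for repeated measures the main analysis. Include every randomised participant with any post-baseline value, all four follow-up visits, arm, visit and arm by visit, with baseline as covariate. Report arm contrasts by visit with 95% confidence intervals.
- **Sensitivity:** keep the complete-case regression as a sensitivity analysis.
- **Deaths:** state how visits after death are treated, since the model would otherwise impute scores implicitly for them.
- **Missing Data:** limit the completely-at-random, no-bias sentence to baseline values, or delete it.
- **Documenting participant withdrawal:** say whether the intention-to-treat statement covers the secondary outcomes.
- **Planning figures:** beside the SD of change, report the baseline-adjusted residual SD and the baseline–follow-up correlation, with confidence limits.

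The cost is revised wording and slightly more analysis, with no new visits or data. The downside is reliance on the missing-at-random assumption, which should be stated.

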## **Statistical Analysis Plan**

## Primary Outcome

The primary outcome of the study is the feasibility of the protocol as defined as ≥80% of participants completing the 8-week protocol. It will be measured by percentage completed the 8-week protocol. If more than or equal to 80% of participants complete the 8-week protocol it will be deemed feasible. Rates of completion will also be compared by treatment arm at the Week 8 time point. Adherence to the study protocol will also be measured as attendance to telerehab sessions and ≥80% attendance will be defined as adherent. Percentage deemed adherent will be compared between the treatment arms at the 8-week time point.

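### The survival analyses censor participants who drop out of the 8-week protocol although the trial keeps following them, and the only between-arm survival method named yields a p-value the plan will not list

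*Protocol*

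**What the plan says.** - **Censoring rule.** Protocol, Missing Data: "Participants that drop out prior to completion of protocol will be right censored for survival analyses". No censoring date is given and dropping out is not defined.
- **Meaning of completion.** Protocol, Statistical Analysis Plan, Primary Outcome: "If more than or equal to 80% of participants complete the 8-week protocol it will be deemed feasible". The Hypotheses section uses the same 8-week definition.
- **Follow-up after withdrawal.** Protocol, Documenting participant withdrawal: "In all circumstances, reasons for withdrawal will be collected and all participants will be followed through" to the end of the trial, "as the main analysis will be an intention to treat analysis". The section makes this subject to the participant's continued consent.
- **Data collected.** Table 1 has a row "Survival and Progression-Free Survival", marked at weeks 4, 8, 12 and 26.
- **Survival methods.** Protocol, Statistical Analysis Plan, Secondary Outcomes: times to all-cause death, disease-specific death and disease progression "will be analyzed using Kaplan Meier estimators and logrank tests". The last paragraph of that section adds that "p-values will not be listed" and that 95% confidence intervals will be used instead.

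**The concern.** Leaving an 8-week rehabilitation programme does not end observation of death or progression. A participant who stops therapy at week 4, stays in follow-up and dies at week 15 has a death on record that the censoring rule would leave out.

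The loss is unlikely to be random. The withdrawal reasons in the protocol include becoming unable to continue the intervention or visits, and medical conditions that put the participant at risk. In people with glioma both relate to prognosis, whereas Kaplan-Meier and log-rank methods require censoring unrelated to the risk of the event. Only one arm receives live therapy sessions, so dropout may also differ by arm. In that case the comparison is affected as well as the level of the curves.

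The second problem is one of reporting. A log-rank test gives a statistic and a p-value, not an estimate with an interval. The one between-arm survival method named therefore produces a result that the same section says it will not show.

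One objective of the pilot is to test whether survival, among other outcomes, can be measured for a definitive trial, so the rule could be carried forward.

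**Working it through.** **1. The passages side by side.** The censoring rule turns on completing the protocol, which the document ties to 8 weeks. The withdrawal section keeps withdrawn participants under observation, and Table 1 collects survival to week 26. Trial Safety, Fidelity and Implementability Analyses lists dropouts separately from losses to follow-up, so the two terms are not used as synonyms there. For a participant who leaves the protocol but still consents to follow-up, the censoring rule and the follow-up rule cannot both be applied.

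**2. The plan's own figures.** The sample size reproduces: 0.33 × 163 = 53.8 and 163/3 = 54.3, both rounding to 54, or 27 per arm. No event count, hazard ratio or power is stated for survival, so there is no survival figure to reproduce. The 80% criterion allows at most 10 dropouts: 44/54 = 81.5% passes and 43/54 = 79.6% fails.

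**3. Illustration of the bias (all rates assumed).** Ten of 54 participants drop out at week 4, so d = 10/54 = 0.185. Completers have 26-week risk q, with constant weekly hazard λ = −ln(1 − q)/26. After week 4 the dropouts' hazard is h × λ.

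- Risk with everyone followed: 1 − e^(−4λ) × [(1 − d)e^(−22λ) + d·e^(−22hλ)]
- Kaplan-Meier risk with dropouts censored at week 4: 1 − e^(−26λ) = q
- Events counted under the rule: 54 × {1 − e^(−4λ) + e^(−4λ)(1 − d)(1 − e^(−22λ))}

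Example with q = 10%, h = 4: λ = 0.00405, e^(−4λ) = 0.984, e^(−22λ) = 0.915, e^(−88λ) = 0.700. The true risk is 1 − 0.984 × (0.815 × 0.915 + 0.185 × 0.700) = 13.9%, against 10% shown.

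| Completer risk q (= censored estimate) | h | Risk, all followed | Understated by (points) | Expected events, all followed | Events counted |
|---|---|---|---|---|---|
| 5% | 2 | 5.7% | 0.7 | 3.1 | 2.3 |
| 5% | 4 | 7.1% | 2.1 | 3.9 | 2.3 |
| 10% | 1 | 10.0% | 0 | 5.4 | 4.6 |
| 10% | 2 | 11.4% | 1.4 | 6.2 | 4.6 |
| 10% | 4 | 13.9% | 3.9 | 7.5 | 4.6 |
| 20% | 2 | 22.5% | 2.5 | 12.2 | 9.1 |
| 20% | 4 | 26.4% | 6.4 | 14.3 | 9.1 |

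For h = 2 to 4 the rule discards about 25% to 41% of expected events. At h = 1 there is no bias, but events are still lost.

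**4. Unequal dropout with no true effect (assumed).** In both arms 30% of participants are frail, with h times the hazard of the rest, whose 26-week risk is 10%. One arm loses all its frail participants at week 4 (30% dropout), the other one-sixth of them (5%). Average dropout is 17.5%, so the trial would still be called feasible. Let a = 0.7e^(−4λ), b = 0.3e^(−4hλ), and c = the share of frail participants censored. The Kaplan-Meier risk is 1 − (a + b) × [a·e^(−22λ) + (1 − c)b·e^(−22hλ)] / [a + (1 − c)b].

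- h = 4: 11.3% (c = 1) against 16.6% (c = 1/6); the true risk is 17.3% in both (c = 0).
- h = 2: 10.4% against 12.4%; the true risk is 12.7% in both.

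The arm with more dropout looks better by 2.0 to 5.3 points when nothing differs.

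**5. Log-rank against the reporting rule.** The section names Kaplan-Meier curves, which give within-arm estimates with confidence intervals, and the log-rank test, which gives a p-value. It names no hazard ratio or risk difference. With p-values withheld, the only named between-arm survival method leaves nothing to report.

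**The case against.** The strongest reply is that dropping out was meant as loss to follow-up. The Sample Size section says loss to follow-up will be analysed as the primary outcome, which suggests the authors nearly equate the two. On that reading the rule is ordinary censoring at last contact. Follow-up after withdrawal also depends on consent, so some dropouts will have nothing to observe. This stands in part: for people who withdraw consent or are truly lost, censoring at last known status is correct. But the sentence speaks of protocol completion, gives no censoring date, and sits beside a section that lists dropouts and losses separately.

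A second reply is that little rests on these curves. Survival is not among the listed secondary outcomes, the analyses are called hypothesis generating, and 27 per arm gives wide intervals in any case. At an assumed 16% risk, the 95% half-width of the arm difference is 1.96 × √(2 × 0.16 × 0.84/27) = 0.196, about 20 points. That stands, and it limits the severity.

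Readers might infer three stronger things that the document does not support:

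- *That a safety harm would be hidden.* Death is a serious adverse event, such events are recorded to the 26-week visit, and serious events are to be compared between arms by Poisson regression. The censoring sentence covers only the survival analyses.
- *That no survival estimate could be reported.* Within-arm Kaplan-Meier estimates with intervals remain available.
- *That chart review already supplies survival data.* The chart review described in the protocol is for baseline characteristics.

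**Conclusion.** The concern holds in limited form. As worded, the Missing Data rule conflicts with the follow-up rule and with Table 1. It discards events observed in participants who leave the protocol but remain in follow-up, and it can bias the curves and the arm comparison because the listed withdrawal reasons relate to prognosis.

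It does not follow that survival is certain to be overstated. The document gives no death, progression or dropout rates. The figure of about 0.7 to 6 percentage points assumes 10 dropouts at week 4, completer risks of 5% to 20%, and a hazard two to four times higher after dropout. With non-informative dropout the bias is zero and only events are lost.

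The clash between the log-rank test and the no-p-value rule is real but smaller. Overall severity is low to moderate: survival is exploratory, but the correction is cheap and changes what the survival analysis reports.

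**What to change.** 1. **Missing Data.** Replace the censoring sentence. Deaths and progressions count to week 26 regardless of protocol completion. Censor only at the last date known alive (for death) or at the last disease assessment (for progression), including for participants who withdraw consent or are lost.
2. **Statistical Analysis Plan, Secondary Outcomes.** In place of the log-rank test, report a between-arm estimate with a 95% CI: the 26-week Kaplan-Meier risk difference or a hazard ratio.
3. **Endpoint name.** The same section analyses time to disease progression while Table 1 lists progression-free survival. Align the former with Table 1, with death counted as an event.

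The cost is an amendment to protocol wording, plus obtaining last known status, within existing consent, for about 10 participants if completion is near 80%. Nothing changes in the sample size, visits or primary outcome.
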